8.3.7 Protocol violations

Any protocol violations will be logged and reported to the sponsor within 10 working days. Violations generally increase risk or decrease benefit, affect the subject's rights, safety, or welfare, or the integrity of the data.

8.3.8 Intercurrent events

Healing-related reoperation (e.g., for refracture, deep infection requiring implant removal, or nonunion) will be treated as an intercurrent event for the primary endpoint. In the primary analysis, participants will be censored at the last radiographic assessment prior to the intercurrent event. Sensitivity analyses will assess robustness using conservative assumptions, including classifying healing-related reoperation as not united within the follow-up window.

8.3.9 Patient discontinuation

All premature discontinuations are registered in the eCRF.

8.3.10 Missing data

To avoid missing data all required fields in the eCRF are mandatory and the researcher is informed of missing or wrong input during the entry phase. All data is sought to be put into the eCRF during the follow-up visit or immediately after and no later than 10 days after the visit. In this way participants can be contacted in due time in case of missing information. The reason for any missing data will be investigated and reported.

Because the primary endpoint is assessed at discrete radiographic time points, time to union will be analyzed using an interval-censored time-to-event framework. Therefore, no imputation of union time will be performed. Missed radiographs will widen the censoring interval where subsequent images are available; participants without radiographic confirmation of union will be treated as right-censored at their last evaluable radiograph. Missing data for secondary outcomes will be handled as specified in the SAP.

9 Risk analysis

A risk–benefit analysis of the study and the devices has been performed in accordance with ISO 14971 and ISO 14155.

9.1 Treatment-related risks

The risks in this study are associated with (1) the general risks of operative treatment for pediatric diaphyseal forearm fractures and (2) study-related procedures.

Anticipated adverse events (AEs) that may occur as a direct result of the treatment, general anesthesia, and the devices are identified and listed in Section 7.2.6. These risks are inherent to the standard management of fractures requiring surgical stabilization and would be present irrespective of study participation.

Standard treatment using titanium elastic intramedullary nails (TEN) typically includes forearm radiographs at:

- Preoperative / injury
- Intraoperative – using fluoroscopy
- Postoperative
- At FU-visits after 2 and 6 weeks and before implant removal (6-12 months).

9.2 Study disadvantages

Participation in the study involves additional outpatient follow-up visits. Participants will attend approximately 7–9 follow-up (FU) visits, which is 3–5 more visits than typically required with standard care. This increased visit burden may be considered a disadvantage. However, in our pilot study, parents demonstrated high adherence and were willing to attend all scheduled visits.

A potential disadvantage is a longer time to radiographic union and/or a longer restriction from higher-risk activities. Parent acceptability of a potential delay was explored in the pilot cohort by asking the maximum additional weeks beyond the usual 6-week restriction they would accept to avoid a second implant removal operation, and this perspective informed how we frame and communicate the study trade-off.

9.3 Study-related risks

Based on previous studies of the Aactiva IM-Nail™ [7,38], we anticipate that the risk of complications with bioabsorbable intramedullary nails (BIN) is comparable to, or potentially lower than, that observed with titanium elastic intramedullary nails (TEN).

9.3.1 Radiation

During follow-up, AP and lateral radiographs of the forearm will be obtained to assess fracture alignment and to evaluate the study's primary outcome. Compared with standard care, an additional 3–5 two-view forearm radiographic examinations are expected during follow-up.

Radiation exposure from extremity radiography is very low. A typical effective dose is approximately 0.001 mSv per projection; thus, a two-view examination (AP + lateral) is approximately 0.002 mSv. The cumulative additional effective dose is therefore estimated to be approximately 0.006–0.010 mSv. For context, The Danish Health Authority (Sundhedsstyrelsen) states that the average person in Denmark receives about 4 mSv per year from ionising radiation from all sources, most of it from natural background radiation. The additional study-related dose therefore constitutes only a very small fraction of annual background exposure and remains well below 0.1 mSv.

All imaging will be performed using pediatric low-dose protocols in accordance with the ALARA (As Low As Reasonably Achievable) principle, with collimation and shielding as appropriate. No CT imaging is required for study purposes.

9.3.2 Breakage of Aactiva IM-nail

Two cases have been reported worldwide in which a small fragment of the implant was sheared off by the sharp edge of the fracture, necessitating secondary surgery for fragment removal [38]. The Technique Guide for the Aactiva IM-Nail™ has subsequently been revised to emphasize additional caution when advancing the nail across the fracture site and to recommend only light hammer blows.

9.3.3 Fracture re-angulation

There may be an increased risk of fracture re-angulation when using BIN due to the greater flexibility of the implant. This risk is mitigated by immobilization in a circumferential above-elbow cast for 4 weeks, in accordance with the Technique Guide for the Activa IM-Nail™.

9.4 Loss of privacy

There is a risk that participants' private and confidential medical information could be disclosed, resulting in a breach of confidentiality. Measures to minimize this risk are described in Section 9.5.

9.5 Actions to minimize increased risks

- General treatment-related risks are present regardless of study participation and will be managed according to standard of care at the study site.
- The potential risk of fracture re-angulation with BIN is mitigated by immobilization in a circumferential above-elbow cast for 4 weeks, in accordance with the Technique Guide for the Activa IM-Nail™.
- The risk of loss of privacy and confidentiality will be minimized through strict adherence to data protection, safety, and security procedures described elsewhere in this CIP and in applicable SOPs.
- The study will be conducted in accordance with applicable national and international standards and guidelines, including ICH-GCP and ISO 14155. The ethical framework is based on the Declaration of Helsinki, supporting the protection of participant rights, safety, and well-being.

10 Informed consent process

10.1 Where? When? By whom?

All patients and parents will be informed at Herlev Hospital by a delegated member of the research team. Study information will be provided during a preoperative visit as soon as possible after the injury, typically within 3 days. The parents are informed about the option of bringing a support person.

10.2 How?

The information will be provided in an undisturbed setting, allowing sufficient time for discussion and questions. Study information will be provided using plain and understandable language and may be supported by age-appropriate materials (e.g., short videos and toys) to facilitate communication with the child and the parents. The nature of the study, its purpose, the procedures involved, the expected duration, potential risks and benefits, and any discomfort associated with participation will be explained.

In this pediatric study, the parents will receive face-to-face study information and provide written informed consent using the study-specific participant information and electronic informed consent form (eICF). The child will also be informed orally in an age-appropriate manner. Assent will be obtained from any child considered capable of understanding the basic information provided.

The parents will be informed that their child's medical records and radiographs will be accessed by authorized individuals involved in the study (see Section 12). Written informed consent will be obtained from the parents before any study-specific procedures or assessments are performed.

The parents will be provided with the study-specific participant information and eICF, as well as the general information on participation in health research issued by the Danish National Committee on Health Research Ethics, to support an informed decision regarding study participation.

10.3 Patient and Public Involvement - Involvement of children and parents from the pilot study

To improve feasibility and participant understanding before study start, children and parents who participated in the pilot study was invited to provide structured feedback on the randomized trial design and participant-facing materials. This activity was intended as user-testing/advisory input to refine procedures and communication; no clinical outcomes data was collected.

Pilot parents helped inform the clinically acceptable non-inferiority margin by responding to a short acceptability question on the maximum additional waiting time to resume higher-risk activities (beyond the typical 6 weeks for metal implants) that they would accept in exchange for avoiding a second implant removal operation.

Feedback also focused on (1) clarity and readability of the parent information sheet and age-adapted child assent materials, (2) acceptability and understanding of the randomized design, including the rationale for random and equal allocation between treatments, and (3) understanding and acceptability of the proposed blinding procedures and how these are explained to families.

Input was collected via an online questionnaire and optional short semi-structured interviews over phone. Findings was used to revise materials and, where relevant, inclusion procedures. Participation was voluntary and will not affect current or future care; feedback is handled confidentially and reported in aggregated form.

Secondary outcomes are based on the CORE-Kids core outcome set for childhood limb fractures by Marson et al. [44], which was developed using a Delphi consensus process with active involvement of children and parents to ensure the selected outcome domains reflect patient- and family-priorities.

10.4 Voluntariness

Parents and children will be informed that participation in the study is entirely voluntary. They may withdraw from the study at any time without providing a reason, and withdrawal of consent will not affect the child's subsequent medical care or treatment.

10.5 Assessor

When inviting the family to the preoperative visit, the parents will be informed that they may bring an accompanying person (e.g., a support person) to the visit.

10.6 Consideration time

Unstable or displaced diaphyseal forearm fractures typically do not require emergency surgery; however, timely treatment is generally preferred. Surgical planning also requires time for the treating team to prepare for the specific procedure. Therefore, parents will be asked to provide informed consent as soon as possible and no later than the day before surgery.

In most cases, parents will have at least 24 hours to consider participation. In cases where surgery is indicated and can be performed promptly (e.g., due to clinical urgency or available operating room capacity), consideration time may be shorter, but not less than 2 hours whenever feasible. Treatment

will not be delayed for study purposes; if the family declines or is unable to decide within the available timeframe, the child will be treated per standard care and not enrolled.

10.7 Electronic Informed consent form (eICF)

Parents will indicate their willingness to allow their child to participate in the study by signing and dating an ethics committee (EC) approved electronic informed consent form (eICF). The eICF will be administered via REDCap-link sent to the parent's personal electronic mailbox (borger.dk) which requires identification login with secure "MitID". The consent form will automatically be signed and dated on behalf of the research team and retained as part of the study records.

The signed eICF will be filed, and a copy will be provided to the parents via secure electronic mail. A paper version of the informed consent form will be used if parents are unable to complete the eICF electronically.

11 Adverse event reporting

Sufficient safety data will be collected on adverse events (AEs) related to the injury, surgical procedure, implant use, and fracture healing, including information on implant revision and any required secondary surgery (i.e., complications). Detailed definitions of reportable AEs are provided in Section 7.2.6 of this CIP.

11.1 Definitions

In accordance with ISO 14155, adverse events (AEs), serious adverse events (SAEs), adverse device effects (ADEs), serious adverse device effects (SADEs), and device deficiencies are defined in the following sections. A flowchart illustrating AE categorization is provided in Figure 7.

11.1.1 Adverse event

An AE is defined as any untoward medical occurrence, unintended disease or injury, or untoward clinical signs (including abnormal laboratory findings) in patients.

11.1.2 Serious adverse event

A SAE is defined as any AE that:

- led to death
- led to a serious deterioration in health of the patient that either resulted in
- a life-threatening illness or injury, or
- a permanent impairment of a body structure or a body function, or
- inpatient or prolonged hospitalization, or
- a medical or surgical intervention to prevent life-threatening illness or injury or permanent impairment to a body structure or a body function

Note: Planned hospitalization for a pre-existing condition or a procedure required by the CIP, without serious deterioration in health, is not considered as a SAE.

The definition of an AE does not imply that there is a relationship between the AE and the device or procedure under investigation.

11.1.3 Adverse device effect and serious adverse device effect

An ADE is defined as any AE related to the use of an investigational medical device.

Note 1: This definition includes AEs resulting from insufficient or inadequate instructions for use, deployment, implantation, installation, or operation, or any malfunction of the investigational medical device (see also section 11.1.5 for definition of device deficiency).

Note 2: This definition includes any event resulting from use error or from intentional misuse of the investigational medical device.

A SADE is defined as any ADE that results in any of the consequences characteristic of a SAE.

11.1.4 Unanticipated (serious) adverse device effect

An unanticipated (serious) ADE (U(S)ADE) is defined as a (S)ADE which by its nature, incidence, severity, or outcome has not been identified in 7.2.3.

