4.6 Current status of research in this area

To assess feasibility and safety, we conducted a prospective preliminary study including 18 children with forearm fractures treated with bioabsorbable intramedullary nails (BIN). No serious adverse events

or serious adverse device effects were observed. All fractures healed, and all children regained normal arm function within 3 months.

An international multicenter study of 76 children treated with the Activa IM-Nail reported few complications. In two cases, a small implant fragment was sheared off by the sharp fracture edge, necessitating secondary surgery for fragment removal. The Activa IM-Nail Technique Guide has subsequently been revised to emphasize additional caution when advancing the nail across the fracture site and to recommend only light hammer blows [38].

In Finland, the Activa IM-Nail has been investigated since 2011 in a randomized controlled trial comparing BIN with TEN. Both short- and long-term follow-up demonstrated similarly good outcomes [7,30].

To date, no studies have evaluated differences in time to bone union when comparing BIN with TEN. Furthermore, time to healing in PDFF has not been rigorously investigated in a prospective setting.

5 Primary and secondary objectives

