7.2.3 Pain and discomfort

At each FU visit, pain and discomfort and use of medication is evaluated and documented.

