7.2.6 Complications from the injury and its treatment (adverse events)

This section describes all anticipated AEs, SAEs, ADEs, and SADEs. Further definition and description, see section 11.

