7.2.6.4 Re-operation

Re-operation risk is anticipated at 0.1-0.5% due for any reason following the procedure.

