8.2.6 Drop rate / sample size inflation

In our pilot study, 1/18 (~5%) participants were lost to follow-up. For the present RCT we apply a total inflation of 10%, comprising ~5% loss to follow-up/withdrawal and ~5% intercurrent events affecting the primary endpoint (e.g., healing-related reoperation). Although intercurrent events will be handled in the primary estimand strategy (see Section 8.3), they reduce the number of informative observations for time-to-union and are therefore accounted for in the sample size inflation.

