Appendix 3 - Device table (Investigational device and comparator)

	Investigational device (BIN)	Comparator device (TEN)
Device role in study	Investigational device	Comparator device
Product type / generic name	PLGA bioabsorbable intramedullary nail	Titanium Elastic Intramedullary Nail
Trade name	Activa IM-Nail™	Titanium Elastic Nail (TEN™) System
Manufacturer	Bioretec Ltd., Tampere, Finland	Synthes GmbH, Oberdorf, Switzerland
Specific model(s) used in trial	B-ANIM-27400 Activa IM-Nail™ 2.7 x 400 mm B-ANIM-32400 Activa IM-Nail™ 3.2 x 400 mm	475.9xxS (xx=mm diameter) (sterile “S” variants)
Sizes / range relevant to study	2.0–3.2 mm x 200–400 mm	1.5 mm × 300 mm 2.0–3.0 mm × 440 mm
CE-marked	Yes	Yes
Device class (MDR)	Class III	Class III
Notified Body	DEKRA Certification B.V. (NB 0344)	TÜV SÜD (NB 0123)
Sterile	Yes	Yes
Measuring function	No	No
Reusable surgical device	No	No
Invasive / implantable	Yes / Yes	Yes / Yes
Incorporates medicinal substance / blood derivative	No	No
Incorporates non-viable tissues/cells (human/animal)	No	No
Intended use (high-level)	Intramedullary fixation of pediatric forearm diaphyseal fractures	Bone fixation nails are intended for temporary fixation, correction and stabilization of bones

Target population (IFU)	Pediatric	Recommended for skeletally immature patients
Key contraindications (headline)	
 • Multifragmentary fractures • Metaphyseal or epiphyseal fractures 
General contraindications to internal fixation / use:
 
 • Active or suspected infection 	
Key potential adverse events / residual risks	Infection, malunion/non-union, neurovascular damage, implant migration/loosening/breakage, compartment syndrome, etc.	
Accessories / related components used	BIN system instruments (awl, dilator, inserter, cutter, impactor, etc.)	TEN system instruments (awl, inserter, cutter, impactor, extraction pliers, etc.)
Sterilization / reprocessing notes	Device is delivered in a sterile state and re-sterilization by any method is restricted in the labelling.	Sterile devices: irradiated; single-use devices not to be reused
MRI information	MRI safe	MRI Conditional: non-clinical 3T testing described in IFU
Implant removal	No	Routine removal after bone healing

2048

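### Section 11.1.4 defines unanticipated device effects against the pain section; the list it should cite, 7.2.6, omits Appendix 3 risks and carries an unsourced reoperation rate

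*Protocol*

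**What the plan says.** Protocol 11.1.4 defines an unanticipated (serious) adverse device effect as one whose nature, incidence, severity or outcome "has not been identified in 7.2.3". It is the only definition of this class in the protocol, and the expert review in 11.5 has to apply it.

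Section 7.2.3 is headed Pain and discomfort and opens: "At each FU visit, pain and discomfort and use of medication is evaluated and documented". Its subsections cover the FPS-R, discomfort and pain medication.

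The anticipated events are in 7.2.6, which opens: "This section describes all anticipated AEs, SAEs, ADEs, and SADEs". Section 9.1 and the opening of section 11 also refer to 7.2.6.

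Three further places bear on the content of that list:

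- 7.2.6.4: "Re-operation risk is anticipated at 0.1-0.5% due for any reason following the procedure". No source is given.
- 4.6, on a multicentre series of 76 children treated with the Activa IM-Nail: "In two cases, a small implant fragment was sheared off by the sharp fracture edge, necessitating secondary surgery for fragment removal". The Technique Guide was revised afterwards.
- Appendix 3, whose row of key potential adverse events and residual risks ends: "implant migration/loosening/breakage, compartment syndrome, etc".

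For the sample size, 8.2.6 allows for about "5% intercurrent events affecting the primary endpoint (e.g., healing-related reoperation").

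**The concern.** The unanticipated class is meant to separate new device effects from known ones. It can do so only if the definition points to a list of known effects, the list contains what the sponsor already knows, and any rate in it is credible, since incidence is one of the four tests. As written, the pointer goes to a section with no device effects. Correcting the section number alone would still leave a list that is called complete but lacks risks the protocol names elsewhere, and a reoperation rate with no stated basis.

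At stake is how events are labelled in the 11.5 review and in the final report. A breakage already described in the protocol could be recorded as unanticipated, and so could a listed residual risk such as compartment syndrome.

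**Working it through.** **1. The reference.** No arithmetic applies. 11.1.4 names 7.2.3, which lists no device effect. Taken literally, the condition of not being identified there is met by every ADE and SADE. The statement at the head of 7.2.6 and the references in 9.1 and section 11 all support 7.2.6 as the intended target.

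**2. Is 7.2.6 complete?** Appendix 3 residual risks set against 7.2.6:

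| Appendix 3 | In 7.2.6? |
|---|---|
| Infection | Yes, 7.2.6.2 |
| Malunion/non-union | No |
| Neurovascular damage | Nerve injury, 7.2.6.3 |
| Migration/loosening | No |
| Breakage | Yes, 7.2.6.6 |
| Compartment syndrome | No |

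Re-angulation, raised as a BIN risk in 9.3.3, is already in 7.2.6.1.

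**3. The reoperation figure.** The stated 0.1-0.5% cannot be reproduced, because the protocol gives no count or citation for it. The only reoperation count in the protocol is 2 of 76 BIN children (4.6).

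- Point estimate: 2/76 = 2.63%.
- Exact (Clopper-Pearson) 95% limits: lower, the 2.5% point of Beta(2, 75) = 0.32%; upper, the 97.5% point of Beta(3, 74) = 9.18%.
- Ratios of point estimate to stated range: 2.63/0.5 = 5.3 and 2.63/0.1 = 26.
- Chance of two or more in 76, 1 - (1-p)^76 - 76p(1-p)^75: 0.0027 at p = 0.1%; 0.056 at p = 0.5%.

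So 0.1% is clearly at odds with the series. The upper end, 0.5%, lies above the lower limit of 0.32% and so just inside the interval.

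Sensitivity: assume that the 18 pilot children are distinct from the 76 and had no reoperation (4.6 says they had no serious adverse event or serious device effect). Then 2/94 = 2.1%, exact 95% CI 0.26% to 7.5%, and the two probabilities become 0.0041 and 0.081. The picture is the same.

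**4. What this means with 30 BIN children** (8.2.7). Chance of at least one reoperation, 1 - (1-p)^30:

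| Assumed rate | Expected number | Chance of at least one |
|---|---|---|
| 0.1% | 0.03 | 3% |
| 0.5% | 0.15 | 14% |
| 2.6% | 0.79 | 55% |

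One event is 1/30 = 3.3% of the arm or 1/60 = 1.7% of the trial. Both exceed 0.5%, so no non-zero observed proportion can fall within the stated range.

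**5. The 5% allowance.** It is 10 to 50 times the stated range (5/0.5 and 5/0.1), and 8.3.8 treats healing-related reoperation as the intercurrent event. But it is a rounded inflation for non-informative observations, with reoperation as an example. It is hard to square with 0.1-0.5%, but it is not a second estimate of the same quantity.

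**6. Sample size.** 2 × (1.960 + 1.282)² × 3²/3² = 21.0, rounded up to 22; 22/0.90 = 24.4, rounded up to 25. Both stated figures reproduce, and neither uses the 0.1-0.5%.

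**The case against.** The strongest reply is that the wrong section number is clerical. The right one is recoverable from three other places, a medical expert reviews every classification, and the literal reading flags too much, so it hides nothing. No stated safety action hangs on the label. Every SAE goes to the PI, sponsor and EC, with the form due within 24 hours (11.3). Every ADE or SADE goes to the manufacturer (11.5). The pause criteria are a refracture rate above 25% and mean BIN healing above 12 weeks (19.1). All of this stands, and it limits the consequence to classification. It does not make the definition correct.

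On the rate, the two operations predate the Technique Guide revision, concern BIN only and are just two events. 7.2.6.4 does not say that its figure is specific to BIN. This also stands, but the protocol neither presents 0.1-0.5% as a post-revision estimate nor gives data for one.

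A reader might infer three stronger things, none of which the document supports:

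- That 0.1-0.5% flatly contradicts a 5% reoperation rate. The 5% is a planning allowance for intercurrent events, not a reoperation rate.
- That the stated risk is at least five times too low. The factor of five is a ratio to a point estimate whose interval includes 0.5%.
- That the first reoperation would automatically count as above the anticipated incidence. The protocol sets no rule for comparing observed with anticipated incidence, and at a true rate of 0.5% one event in 30 children has a 14% chance of occurring.

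**Conclusion.** The point holds as a defect in the safety definitions. The reference in 11.1.4 is wrong as written, with certainty. The list in 7.2.6 omits three entries that Appendix 3 gives as residual risks: malunion/non-union, migration/loosening and compartment syndrome. The reoperation figure of 0.1-0.5% is unsourced and fits poorly with the protocol's only count, 2/76 = 2.6% (exact 95% CI 0.3% to 9.2%): clearly at its lower end, and at its upper end only as a point estimate. That comparison assumes that the pre-revision BIN series is relevant to the trial and that reoperation for any reason includes fragment removal.

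The consequence is misclassification in the adverse event review. It would go too far to say that a real safety signal could not be recognised: the interim review in 19.1 covers all AEs, ADEs, SAEs and SADEs, together with reoperation, loss of reduction and delayed union, whether anticipated or not. SAE reporting, the stopping criteria, the sample size and the primary analysis do not change.

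**What to change.** 1. In 11.1.4, replace 7.2.3 with 7.2.6.
2. In 7.2.6, add the Appendix 3 residual risks now missing: malunion/non-union, implant migration/loosening and compartment syndrome. Re-angulation and breakage are already there.
3. In 7.2.6.4, either give the source of 0.1-0.5% or reconcile it with the two operations in 76 children in 4.6 and with the allowance in 8.2.6. State whether the figure applies to BIN, TEN or both, and that planned TEN removal is not counted. If it is meant to reflect practice after the Technique Guide revision, say so and give the basis.

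The cost is protocol wording only. If the figure is brought into line with 4.6, the stated reoperation risk becomes less favourable. No analysis or recruitment target is affected.
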